Protocol for Comparative Efficacy of Self-directed & Therapist-assisted Telehealth Parent
Training Intervention for Children With ASD

NCT02721381

Based on last approval by MSU IRB on 4/6/2020

Risk to Human Subjects

a. Human Subjects Involvement, Characteristics, and Design

A total sample of 90 children with ASD between the ages 18-96 months and their primary caregivers will be recruited for this study. This sample size was determined to be adequate for maintaining adequate power for the proposed statistical analyses, while allowing for some attrition.

Inclusion Criteria for Families: To be eligible for participation, 1) the child must receive a DSM-V-informed clinical diagnosis of Autism Spectrum Disorder, based on the *Autism Diagnostic Observation Schedule* (ADOS). The diagnosis may be provisional for children under age 3 (typically listed as "at risk for ASD"). Children with this classification will be included as well. (2) The child must fall between the ages of 18 - 96 months at enrollment into the study, which will allow for data collection during the period of early intervention and early childhood special education programming. (3) The parent must understand spoken English as the training materials are presented in English.

Exclusion Criteria for Families: (1) Children with ASD who have a history of significant brain injury or known neurological condition in addition to a diagnosis of ASD, significant sensory impairment or major medical problems. These children and their families may require very specific adaptations to the treatment and thus the results will not be representative of children with ASD. This will be determined through review of medical records, diagnostic reports and parent interview. Criteria and data sources for identifying participants are outlined below.

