Assignment to Study Group: Participating children and their primary caregivers will be assigned to one of three groups. Participants will be stratified by age (18-35 months; >36 months) and developmental quotient (DQ<55; DQ ≥55) at project enrollment, prior to being randomized. After stratification, participants will be randomly assigned to the one of the three groups using random permuted blocks of 6. This approach has been shown to yield groups that are closely balanced with regard to size and relevant pre-treatment characteristics. All pre-treatment assessments will be collected prior to randomization to prevent bias during testing based on knowledge of future group placement.

b. Sources of Materials

The sources of data for this study will include: (1) direct assessment of child functioning using standardized assessments; (2) completion of standardized questionnaires by parents; (3) written survey completion by parents; and (4) videotaped coding of treatment processes. All data will be used exclusively for research purposes. All surveys and interviews will use codes rather than subject names. Only the PI and primary research team members will have access to subject identities. Procedures to minimize risk of loss of confidentiality are presented below.

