Aim 3: To examine whether pre-treatment parenting stress moderates the effects of *ImPACT Online* on parent fidelity and parent self-efficacy at post-treatment. Pre-treatment parenting stress will be included in the MLM models as a covariate. The pre-treatment parenting stress by time interaction will be used to determine whether pre-treatment parenting stress moderates change over time, irrespective of treatment group. The three-way interaction of pre-treatment parenting stress, group, and time will be used to examine whether the relationship between group assignment and change over time (i.e., group slopes) varied by pre-treatment parenting stress. A significant interaction will be followed up by simple slopes analyses.

Aim 4: To examine whether gains in parent fidelity (or parent self-efficacy) and child intentional communication at post-treatment mediate the effects of the *ImPACT Online* on child verbal language at the 3-month follow-up. We will conduct two serial mediation analyses using the PROCESS macro in SPSS to examine whether gains in parent fidelity (Mediator 1) and child intentional communication (Mediator 2) at post-treatment mediate the effect of *ImPACT Online* in child outcomes at follow-up. A second serial mediation analysis will be conducted to examine whether gains in parent self-efficacy (Mediator 1) and child intentional communication (Mediator 2) at post-treatment mediate the effect of *ImPACT Online* in child outcomes at follow-up.

Aim 5 (exploratory): To identify predictors of parent adherence to *ImPACT Online* for the two treatment groups. This exploratory aim will be addressed using a multiple regression approach in which level of therapist support (self-directed versus therapist assisted) and three individual-level factors (computer and internet fluency, expectancies of treatment, and treatment acceptability) serve as primary predictors of parent adherence. We will also examine sociodemographic variables as predictors as well.

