Power Analysis. A series of power analyses were conducted using Borm, Fransen, & Lemmens⁸⁹ method for estimating sample size for analyses including a covariate. This approach takes into account the degree of association between the covariate and the outcome (r) by adjusting the required sample size required for an analysis without a covariate by $1 - r^2$ and then adding one extra participant per group. In our case, the covariate is the outcome variable as assessed at the pre-test. Analyses predicting parent fidelity (i.e., Aims 1 & 2) assumed a T1 to T2 correlation in fidelity of $r = .35$, and for self-efficacy, the T1 to T2 correlation was assumed to be $r = .75$. Across the aims involving parent fidelity we found that a sample size of 90 participants would provide 80% power to detect moderate to large effects of treatment condition (e.g., Cohen's $f = .32$). For parent self-efficacy a sample of 90 would provide 90%

power to detect moderately sized treatment effects (e.g., $f = .25$). For the child language variables we assumed a correlation between pretest and follow-up of approximately $r = .65$ for each of the three measures. Analyses predicting child language variables at follow-up controlling for pretest language scores (i.e., Aims 2 & 4) indicated that a sample size of 90 participants will have approximately 90% power to detect a moderate effect size ($f = .25$) for treatment condition.

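### The 90% power assigned to Aims 2 and 4 is for a treatment effect on language; Aim 4's serial indirect effects have no stated power, and the 90% itself recomputes to about 78–79%

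*Combined protocol and SAP*

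**What the plan says.** The protocol's first section sets the sample size: "A total sample of 90 children with ASD between the ages 18-96 months and their primary caregivers will be recruited". It calls this adequate "while allowing for some attrition", without giving a rate. Families are "randomly assigned to the one of the three groups using random permuted blocks of 6".

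The Power Analysis section of the Statistical Analysis Plan uses a method "for estimating sample size for analyses including a covariate". The method works by "adjusting the required sample size required for an analysis without a covariate by $1 - r^2$ and then adding one extra participant per group". Three statements follow, all for N = 90:

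- Parent fidelity, r = .35: the sample "would provide 80% power to detect moderate to large effects of treatment condition", with f = .32 as the example.
- Parent self-efficacy, r = .75: 90% power at f = .25.
- Child language, r = .65 for each of three measures: about 90% power at f = .25 for treatment condition. This is assigned to "Analyses predicting child language variables at follow-up controlling for pretest language scores (i.e., Aims 2 & 4").

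Aim 2 is a three-group ANCOVA of language at follow-up. Aim 4 is different: "We will conduct two serial mediation analyses using the PROCESS macro in SPSS". In each model the effect runs from group to a parent mediator (fidelity in one, self-efficacy in the other), then to child intentional communication, then to language.

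**The concern.** A serial indirect effect is a product of three paths. Power to detect a difference in mean language between groups says nothing direct about power to detect that product. The Power Analysis gives no effect size for mediator 1 to mediator 2, none for mediator 2 to language, and no power for either indirect effect. Yet Aim 4 is listed beside a 90% figure and, unlike Aim 5, is not labelled exploratory.

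What is at stake is how a null Aim 4 result can be read. From a test with 90% power it would count against the proposed mechanism; from a test with 20–60% power it would say little. The documents do not say how a null result will be interpreted, which is a further reason for the stated power to be right.

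The same sentence also carries Aim 2, so its arithmetic needs checking as well.

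**Working it through.** **Inputs.** From the plan: N = 90, three groups, and the f and r values above. Assumed: equal groups of 30, two-sided alpha .05 (the plan states no alpha), no attrition, and values for the later paths.

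**Step 1: the plan's own figures.** Under the plan's rule, 90 adjusted participants correspond to N_u = (90 − 3)/(1 − r²) without a covariate. Power then comes from the noncentral F with 2 and N_u − 3 df and λ = N_u f². As a check, the direct ANCOVA uses λ = 90 f²/(1 − r²) with 2 and 86 df.

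| Outcome | 1 − r² | N_u | λ, plan's rule | Power, plan's rule | λ, ANCOVA | Power, ANCOVA | Stated |
|---|---|---|---|---|---|---|---|
| Fidelity, f = .32 | .8775 | 99.1 | 10.15 | 80.9% | 10.50 | 82.1% | 80% |
| Self-efficacy, f = .25 | .4375 | 198.9 | 12.43 | 89.0% | 12.86 | 89.4% | 90% |
| Language, f = .25 | .5775 | 150.6 | 9.42 | 78.1% | 9.74 | 79.0% | about 90% |

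The two parent figures reproduce; the language figure does not. For 90% the unadjusted requirement is 206, so the plan's rule needs 206 × .5775 + 3 = 122 participants (123 for equal groups). Holding N = 90, it would take r of about .76 or f of about .29. Other readings of the language figure give 87.1% (alpha .10), 87.0% (two-sided single contrast, or two groups) and 92.7% (one-sided single contrast). None is within 2 points of 90%.

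**Step 2: the first path of each Aim 4 chain.** The omnibus test gives 82.1% for fidelity and 89.4% for self-efficacy. If all the between-group variation lies along one contrast, the same λ is tested on 1 df, giving 89.3% and 94.4%. That is the most favourable case. An example is therapist-assisted against control with equally spaced arms.

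**Step 3: the later paths.** The documents give no values, so both are assumed to have the same partial correlation ρ. Power for each is from the noncentral t with 84 df and noncentrality √90 × ρ/√(1 − ρ²).

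- ρ = .2: noncentrality 1.94, power .482, squared .232.
- ρ = .3: noncentrality 2.98, power .839, squared .704.
- ρ = .4: noncentrality 4.14, power .984, squared .967.

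**Step 4: joint power.** This is first-path power × (later-path power)², which treats the three tests as independent.

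| Chain and first path | ρ = .2 | ρ = .3 | ρ = .4 |
|---|---|---|---|
| Fidelity, omnibus (.821) | 19% | 58% | 79% |
| Fidelity, best contrast (.893) | 21% | 63% | 86% |
| Self-efficacy, best contrast (.944) | 22% | 66% | 91% |

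A percentile-bootstrap simulation of the product (400 trials per setting, Monte Carlo standard error up to 2.5 points) agrees. Fidelity gives 53–61% at ρ = .3 and 79–90% at ρ = .5; self-efficacy gives 53–62% and 88–94%. The ranges reflect how the three group means are arranged.

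**Step 5: gains.** Aim 4 speaks of gains in the mediators. If these are simple difference scores, the first path has λ = 90 f²/[2(1 − r)]. That is 9.216/1.30 = 7.09 for fidelity and 5.625/.50 = 11.25 for self-efficacy. First-path power is then 65–75% and 85–91% (omnibus to best contrast).

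**The case against.** The sentence says that the 90% is for treatment condition; it does not claim 90% for an indirect effect. Aim labels in this section are loose elsewhere too: fidelity is assigned to Aims 1 and 2, although Aim 2 concerns child outcomes. On that reading the fault is labelling. This is fair, but it leaves Aim 4's actual question with no power statement, so the correction is still needed.

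A reader might go further and infer that 90% is impossible for Aim 4, because the plan puts the first path of the fidelity chain at 80%. The documents do not support that. The 80% is for a three-group effect, and a single contrast at the same f reaches 89%. The self-efficacy chain starts from 89–94%. The f values are examples, not assumed true effects. With strong later paths, about 90% can be reached.

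Nor do the documents support a fixed low ceiling for self-directed against control. First-path power for fidelity in that comparison is 36% if the arms are equally spaced, but 79% if the two treated arms are equal, and the plan gives no spacing.

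On the language figure, the sponsor could reply that the composite outcome may correlate more highly over time than its components. It may, but the plan states .65 for each measure and gives no value for the composite.

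**Conclusion.** The point holds in two parts. First, a power figure for a treatment effect on language is attached to Aim 4, whose serial indirect effects have no stated path sizes or power. On the assumed range of .2 to .4 for both later paths, power runs from about one in five to 79–86% for the fidelity chain, and up to about 91% for the self-efficacy chain with its best contrast. About 90% needs both later paths at roughly .4 to .5 or more, which the plan neither supports nor excludes. Second, the 90% is not obtained from the plan's own inputs even for Aim 2; about 78–79% is.

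The Aim 2 result rests on a two-sided alpha of .05 and no attrition. The Aim 4 figures rest also on the assumed later paths, the independence approximation and the plan's example f values. Attrition, which the protocol expects but does not quantify, would lower all of them.

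**What to change.** Limit the language sentence to Aim 2. Restate its power as about 78–79% at f = .25, or correct and justify the input that produced 90%, such as a higher pretest correlation for the composite. State the alpha used.

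For Aim 4, do one of two things:

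- report simulated power for each of the two serial indirect effects, naming the path sizes, the coding of the three groups, how gains are defined, the interval method and an attrition allowance; or
- state that Aim 4 is exploratory and not powered.

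Removing Aim 4 from the sentence without rechecking the figure would leave 90% standing for Aim 2.

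The cost is a few sentences and a short simulation, with no change to the design. The downside is that the stated figures become less favourable.

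### The stated power of about 90% for child language is about 78% by the plan's own method, correlation and sample size, before any attrition

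*Combined protocol and SAP*

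**What the plan says.** The Power Analysis section takes the sample size needed without a covariate, multiplies it by 1 − r², where r is the correlation of the pretest with the outcome, and adds one participant per group. It then makes three claims for N = 90:

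- Parent fidelity: r = .35, f = .32, power 80%.
- Parent self-efficacy: r = .75, f = .25. The text reads "For parent self-efficacy a sample of 90 would provide 90", the last number being the power in percent.
- Child language: "we assumed a correlation between pretest and follow-up of approximately $r = .65$ for each of the three measures", and the claim is that "a sample size of 90 participants will have approximately 90% power to detect a moderate effect size" of f = .25 for treatment condition. The sentence attaches this figure to Aims 2 and 4.

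The protocol section on Human Subjects Involvement, Characteristics, and Design says of the 90: "This sample size was determined to be adequate for maintaining adequate power for the proposed statistical analyses, while allowing for some attrition". No attrition rate and no significance level are given.

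**The concern.** Self-efficacy and language share the same N, the same f and the same method, and differ only in the assumed correlation. Because the method works through 1 − r², they cannot both have about 90% power. At least one figure must be wrong, and the weaker correlation belongs to language.

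This matters because verbal language is the only outcome the SAP names for Aim 2 and is the endpoint of both mediation models in Aim 4. A reader who takes the 90% at face value will give a null language result more weight as evidence of no effect than the design supports.

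Two related points concern the same statement. The figures use all 90 participants, so they contain no allowance for the attrition that the protocol says is covered. And the language figure is power for a group difference, whereas Aim 4 tests serial indirect effects.

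**Working it through.** **Inputs**

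- N = 90, from the Power Analysis section.
- Three groups, from Assignment to Study Group: "participants will be randomly assigned to the one of the three groups using random permuted blocks of 6". Equal allocation is assumed, giving 30 per group.
- r and f for each outcome, from the Power Analysis section.
- Test: the omnibus F with 2 numerator degrees of freedom, since the SAP's Aim 2 compares three conditions by ANCOVA.
- Alpha: not stated; .05 assumed.

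**Formula.** Inverting the plan's rule gives the uncovaried sample size to which 90 participants are equivalent:

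N_eff = (90 − 3) / (1 − r²)

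Power is that of a three-group one-way F test with noncentrality λ = N_eff × f² and degrees of freedom 2 and N_eff − 3.

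**The plan's three figures**

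| Outcome | r | 1 − r² | N_eff | f | λ | Power | Stated |
|---|---|---|---|---|---|---|---|
| Fidelity | .35 | .8775 | 87/.8775 = 99.1 | .32 | 10.15 | 80.9% | 80% |
| Self-efficacy | .75 | .4375 | 87/.4375 = 198.9 | .25 | 12.43 | 89.0% | 90% |
| Language | .65 | .5775 | 87/.5775 = 150.6 | .25 | 9.42 | **78.1%** | about 90% |

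The first two agree with the plan to about one point, which supports the reading of the method and the assumed alpha. Only language fails, by about 12 points.

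**Can another reading rescue it?** Language power at N = 90 under variants:

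- Without the extra participant per group: 79.6%.
- Direct ANCOVA F with 2 and 86 degrees of freedom, λ = 90 × .0625/.5775 = 9.74: 79.0%.
- Alpha .10: 86.4%. Fidelity then becomes 88.5% and self-efficacy 93.9%, so the two matches are lost.
- Alpha .025: 68.9%. Alpha .01: 56.1%.
- A single 1-df contrast on all 90: 87.0%. Two groups sharing the 90: 86.6%.

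None reaches 90%.

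**What would deliver the stated power at f = .25 and r = .65**

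- 90%: the uncovaried N is 205.5, or 207 in equal groups. 207 × .5775 + 3 = 122.5 (206 gives 122.0), so about 122 to 123 participants.
- 80%: the uncovaried N is 157.2, or 159 in equal groups. 159 × .5775 + 3 = 94.8, so about 95.
- Holding N = 90, 90% power needs f of about .293 at r = .65, or r of about .76 at f = .25.

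**Attrition.** The rates are assumptions, because the protocol gives none:

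| Loss | N | Language | Fidelity |
|---|---|---|---|
| 0% | 90 | 78% | 81% |
| 10% | 81 | 73% | 76% |
| 20% | 72 | 67% | 70% |

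**Aim 4.** The figure is for the effect of treatment condition on language. Aim 4 asks whether the effect passes through parent fidelity (or self-efficacy) and then child intentional communication. That power depends on the paths from treatment to the first mediator, from the first to the second, and from the second to language. The section assumes no values for these paths.

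**The case against.** The strongest reply concerns the composite. The .65 is assumed for each measure, but if the measures correlate above .50 the SAP analyses an equally weighted sum of three z-scores, which may be more stable over time than its parts. Let k be the between-measure correlation at one time and c the between-measure correlation across time. The composite correlation is then (3 × .65 + 6c)/(3 + 6k). At k = .50, c = .325 gives .65 (78% power), c = .40 gives .725 (86%) and c = .45 gives .775 (92%). At k = .60, c = .40 gives .66 (79%) and c = .50 gives .75 (89%). So about 90% is attainable for the composite. What stands is that 78% is tied to the stated per-measure correlation. But the plan gives neither k nor c, makes no such argument, and forms the composite only if the correlation condition is met.

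On attrition, the SAP commits to intention-to-treat, follow-up of those who withdraw, and EM imputation where complete data are needed, so 90 is the right count of participants in the analysis. The multilevel models for parent outcomes also keep partial data, which makes a completers-only figure pessimistic for fidelity. Both points are fair. Still, imputing a missing follow-up language score does not restore the information lost, and the stated powers contain no margin for it.

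On Aim 4, the sentence does limit its figure to treatment condition, and naming the aim may only identify which analyses predict language. That makes it a matter of clarity, but a reader could still take Aim 4 to be powered.

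Finally, 78% is close to the 80% accepted for fidelity, and the primary hypotheses sit with Aim 1, whose figures reproduce. This shows that the sample size is not thereby inadequate. It does not make the stated 90% correct.

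**Conclusion.** The concern holds. On the plan's own method, correlation, effect size and N, power for child language is about 78% (79% by direct ANCOVA), against about 90% stated. The chance of missing a true f = .25 effect is about 22%, roughly double the 10% implied. The result assumes alpha .05, equal allocation and the omnibus three-group test; the plan's other two figures reproduce under the same assumptions. It applies to r = .65 as stated. A composite correlation of about .76 would restore 90%, but the plan does not claim one. Attrition would lower the figure further by an amount that cannot be fixed without a rate. The attrition and Aim 4 points are accurate but secondary to the arithmetic.

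**What to change.** In the Power Analysis section:

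1. Replace the language figure with about 78% power for f = .25 at r = .65, and add that 90% is reached only for f of about .29. Alternatively, state and justify a composite pretest to follow-up correlation of at least .76.
2. State the alpha used.
3. Give all three powers at the expected number of completers, with the assumed rate, or remove the attrition clause from the protocol's sample-size sentence.
4. Remove Aim 4 from the sentence, because the figure does not apply to an indirect effect.

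The cost is wording and a less favourable stated figure. No participants are added, and the design and analyses do not change.
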